***Primary Aim 1. Calculate positive predictive value for patients who have EC/EG then undergo EGD.***

For patients who are predicted to be positive via EsoCheck/EsoGuard to undergo EGD. The estimated EGD positive rate for Strategy B is  $\Pi_B = PP/(PP+PN)$ .

$\Pi_B$  will be calculated and reported with 95% confidence intervals.

***Primary Aim 2. Calculate proportion of patients who have negative EC/EG and are also confirmed to be negative for BE when they undergo EGD.***

### Study population and justification of sample size:

The prevalence of BE in male patients with chronic GERD symptoms who have two other risk factors is 7-10%.(21) A study that performed EGD on 822 men undergoing colonoscopy reported that up to 7% of those without GERD who met criteria similar to what we will use for this study had BE.(25) Furthermore, using the M-BERET BE risk prediction model developed at the University of Michigan, we tested various scenarios that fit our inclusion criteria and found the prevalence of BE for the proposed study population would be expected to be between 4-6%. To be conservative, we have estimated the PPV using a sample size of 500 subjects for the lower

estimated prevalence of 4% and 5%. Our goal is to develop a screening test with a minimal threshold PPV of 20%.

We propose to recruit 500 patients for EC/EG based on the following analysis. If we assume a 5% prevalence of BE in the study population, with a 90/90 sensitivity/specificity for the EsoGuard assay(26), then 70 would undergo endoscopy, of whom 22 would be true positive (true PPV 32% with 95% CI of 26.3-39.1%). If we assume a 4% prevalence of BE in the study population, with a 90/90 sensitivity/specificity for the EsoGuard assay(26), then 66 patients would undergo endoscopy, of whom 18 would be true positive (true PPV 27% with 95% CI of 21.6-33.7%).

The majority of these patients will have a negative EsoGuard assay. Of those with a negative EsoGuard assay, we will recruit up to 100 patients for a research EGD.

Assuming that the sensitivity of EsoGuard is 90% and the prevalence of BE in our population is 5%, the expected rate of missed BE will be 0.5% in EsoGuard negative patients. If we perform EGD on 100 patients then we will be able to estimate a miss rate of 0.5% with a 95% confidence of  $\pm 1.4\%$ . Even if we assume that the sensitivity of EsoGuard is only 80%, then the expected rate of missed BE will be 1% in EsoGuard negative patients. If we perform EGD on 100 patients, then we will be able to estimate a miss rate of 1% with a 95% confidence of  $\pm 2\%$ , i.e. a positive test result defines a population with a 27-fold enrichment for BE versus a test negative population.

The research EGD procedure will be billed to research; therefore, patients will not have to pay for EGD costs if they have a negative EsoGuard assay result. The performance of research EGD on 100 patients with negative EsoGuard assays will allow us to estimate the proportion of BE patients that are missed by an EC/EG strategy in these patients.

400 subjects will be recruited at UH locations. We plan to extend enrollment for this study to other sites by 100 subjects to obtain a planned final enrollment of 500.

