The study team member will initially and purposefully allow the potential subject to “opt-out” of being approached for study inclusion. The study team member will assure the subject that they will not need to participate in the study to receive their scheduled clinical care and they will receive their prescribed medical care whether they decide to participate in the research, or not. If the potential subject is agreeable and found to be eligible, they will be presented with the consenting process by the Human Research Protections Certified member of the research team.

If they agree to participate and have signed and dated the approved informed consent form, they will then be asked to complete the study Questionnaire, Release of Medical Information Form with the study team and then undergo the EsoCheck procedure prior to their scheduled endoscopic procedure.

Once eligibility has been established the study will be explained in detail by one of the study team. Specifically, it will be explained that participation requires the following:

1. Written informed consent to participate in the study.
2. Donation of biofluids or tissue collected during non-endoscopic sampling (EsoCheck Procedure).
3. Signature of “Authorization for Release of Medical Information” form (Appendix G) by affected subjects or their authorized representative to allow researchers to obtain surgical reports, pathology reports, chart summaries, and/or paraffin-embedded tumor blocks and matching H & E slides related to the diagnosis of BE and/or EAC.
4. Completion of a Study Questionnaire that asks questions about reflux symptoms and patient’s attitudes toward non-endoscopic screening.
5. Performance of an EsoCheck procedure; the EsoCheck sample will subsequently be tested with the EsoGuard assay.
6. Patients whose EsoGuard assay results comes back positive, suggesting that they may have BE, will be recommended an EGD and contacted to undergo EGD. This will be a standard of care billable EGD. EsoGuard assay results may take up to two weeks from the date when the sample is obtained. Patients will be contacted by phone and results will be discussed with them. The patient will then have the opportunity to schedule an EGD at their convenience.

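### The planning 95% CIs for the primary PPV are about 40-46% too narrow for the planned estimator; at 4% prevalence the correct interval includes the 20% minimal threshold.

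*Combined protocol and SAP*

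**What the plan says.** Section 9.0, Primary Aim 1, defines the estimated PPV as PP/(PP+PN): EsoGuard-positive patients confirmed by endoscopy (EGD), divided by all EsoGuard-positive patients who had it. The estimate "will be calculated and reported with 95% confidence intervals". No interval method is named.

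Section 9.0, under the justification of sample size, sets a target: "Our goal is to develop a screening test with a minimal threshold PPV of 20"%. The next sentence reads "We propose to recruit 500 patients for EC/EG based on the following analysis". Two scenarios follow:

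- **5% prevalence**, sensitivity and specificity 90% each: "then 70 would undergo endoscopy, of whom 22 would be true positive (true PPV 32% with 95% CI of 26.3-39.1"%).
- **4% prevalence**, same accuracy: 66 endoscopies, "of whom 18 would be true positive (true PPV 27% with 95% CI of 21.6-33.7"%).

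The same section expects prevalence between 4% and 6% from a risk model, describes its choice of 4% and 5% as conservative, and limits research endoscopy to at most 100 EsoGuard-negative patients.

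**The concern.** A proportion near 30% estimated from about 70 patients has a standard error of about 5.5 points, so its 95% interval should reach about 11 points either side. The printed intervals reach about 6.4 and 6.1 points.

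These two intervals are the only precision given for the primary PPV, and they come directly after the 20% goal. Both printed lower limits (26.3% and 21.6%) lie above 20%. A reader would conclude that 500 patients give an interval clear of 20% even at the lower planning prevalence. If the intervals are wrong, that reassurance goes in the 4% scenario, and the reported interval will be nearly twice as wide as planned.

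**Working it through.** **Inputs**, all from Section 9.0: N = 500; prevalence 5% or 4%; sensitivity and specificity 90%; estimator PP/(PP+PN); confidence level 95%.

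**1. Expected counts.** True positives = N × prevalence × 0.9; false positives = N × (1 − prevalence) × 0.1.

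- 5%: 22.5 + 47.5 = 70; PPV = 22.5/70 = 32.1%.
- 4%: 18 + 48 = 66; PPV = 18/66 = 27.3%.

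The plan's counts and point estimates reproduce.

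**2. Reproducing the printed limits.** Wald, Wilson, exact (Clopper-Pearson), Agresti-Coull, Jeffreys and binomial logit intervals at 95% all fail to give them. So do Wald, Wilson and exact intervals at 80% and 90%. What does match is a logit interval for a predictive value with prevalence treated as known:

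var(logit PPV) = (1 − Se)/(Se × n_BE) + Sp/((1 − Sp) × n_nonBE)

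- 4% (18 of 20 with Barrett's positive, 48 of 480 without): 0.1/(0.9 × 20) + 0.9/(0.1 × 480) = 0.00556 + 0.01875 = 0.02431; SE = 0.1559. Logit = ln(18/48) = −0.981. Limits: −0.981 ± 1.96 × 0.1559, which back-transform to **21.65-33.73%** (printed 21.6-33.7%).
- 5% (counts rounded up to 23 of 25 and 48 of 475): variance 0.0222, SE = 0.1490, logit = ln(23/48) = −0.736. Limits: **26.35-39.09%** (printed 26.3-39.1%). Unrounded counts give 25.98-39.00%.

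**3. What that formula leaves out.** For PP/(PP+PN), the large-sample variance of the logit is 1/PP + 1/PN. At 4% this is 1/18 + 1/48 = 0.0764. The known-prevalence variance is the same sum less 1/20 + 1/480 = 0.0521, which gives 0.0243. The subtracted part is the sampling variation in how many patients have Barrett's, about 68% of the total (0.0521/0.0764). The formula suits prevalence fixed from outside, with sensitivity and specificity estimated in verified groups with and without the disease. Here prevalence is only a 4-6% range, and at most 100 of about 430 test-negative patients (500 − 70) have endoscopy.

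**4. Intervals for the planned estimator.**

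| | Printed | Wald | Wilson | Exact |
|---|---|---|---|---|
| 22/70 | 26.3-39.1% | 20.6-42.3% | 21.8-43.0% | 20.9-43.6% |
| 18/66 | 21.6-33.7% | 16.5-38.0% | 18.0-39.0% | 17.0-39.6% |

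**5. Size of the discrepancy.** Printed widths are 12.8 and 12.1 points.

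- 5%: Wilson width 21.3, exact 22.8; ratios 12.8/21.3 = 0.60 and 12.8/22.8 = 0.56.
- 4%: Wilson width 21.0, exact 22.6; ratios 12.1/21.0 = 0.58 and 12.1/22.6 = 0.54.

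The shortfall is therefore about 40-46%. Using n = 1.96² p(1 − p)/h², the printed half-widths h (0.064 and 0.0605) would need about 205 and 208 endoscopies.

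**6. Position of 20%.** At 4% every variant in the table includes 20% (lower limits 16.5-18.0%). At 5% every variant excludes it, with lower limits of 20.6-21.8%.

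**7. If the goal were read as a lower limit above 20%.** These are binomial tail probabilities at the planning PPV, with every EsoGuard-positive patient having endoscopy:

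| | Exact | Wilson |
|---|---|---|
| 5%, n = 70 | at least 22: about 60% | at least 21: about 69% |
| 4%, n = 66 | at least 21: about 24% | at least 20: about 33% |

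**The case against.** **There is no rule to fail.** A reader might infer that the trial misses its own success criterion at 4% prevalence. The documents do not support this. Primary Aim 1 is pure estimation, 20% is called a goal, and nothing requires the lower limit to exceed it. Both expected PPVs (32% and 27%) are above 20%. This stands, so the probabilities in step 7 matter only if the sponsor adopts the lower-limit reading.

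**The effect is confined to the lowest scenario.** This also stands. At 5% the correct interval still clears 20%. At 6%, the top of the plan's own range, expected counts are 27/74 (27 + 47) and the exact interval is 25.6-48.5%.

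**The source of the printed limits is inferred.** The plan names no formula, and the 5% match needs 23 true positives where the plan prints 22; with 22 of 25 and 48 of 475 the formula gives 25.3-38.3%. This is a fair caution about origin. It does not rescue the figures, because no 95% binomial interval tried comes near them.

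**The final analysis is not committed to a wrong method.** This is true: the reported interval will come from observed counts, and Primary Aim 1 names no method. The error lies in the planning figures, so a reader should not infer that the eventual primary result will be miscalculated.

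**Endoscopy uptake is a separate matter.** Section 7.0, item 6, says of EsoGuard-positive patients: "The patient will then have the opportunity to schedule an EGD at their convenience". Section 2.0, Aim 1, says those who are positive will have it. The documents give no uptake figure, so none is used here. Fewer endoscopies would generally widen the intervals further, but the discrepancy exists at full uptake.

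**Conclusion.** The concern holds as a wrong stated figure. For the estimator that Section 9.0 defines, the two planning intervals are about 40-46% too narrow. At 22/70 the interval should be 20.9-43.6% exact (Wilson 21.8-43.0%), and at 18/66 it should be 17.0-39.6% exact (Wilson 18.0-39.0%). The 4% scenario therefore does not exclude the 20% threshold, and the 5% scenario excludes it only narrowly.

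This rests on the plan's own prevalence, sensitivity, specificity and enrolment, and on every EsoGuard-positive patient completing endoscopy. The counts and point estimates are correct. That a known-prevalence formula was used is an inference from the numerical match. The finding does not show that 500 patients are too few, because the plan states no precision or probability requirement against which to judge that.

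**What to change.** In Section 9.0:

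1. Replace both intervals with binomial ones, exact or Wilson: 20.9-43.6% or 21.8-43.0% for 22/70, and 17.0-39.6% or 18.0-39.0% for 18/66.
2. Name the same method for the Primary Aim 1 confidence interval.
3. Acknowledge that at 4% prevalence the expected interval includes 20%.
4. State whether the 20% goal refers to the point estimate or to the lower confidence limit. If the lower limit, give the chance of meeting it for the chosen method (exact about 60% at 5% and 24% at 4%; Wilson about 69% and 33%), and note that these figures assume full endoscopy uptake among EsoGuard-positive patients.

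The cost is a wording change. The stated precision becomes less favourable; no extra patients or procedures are needed.

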### **AIM 2. Confirm that patients who are negative as assessed by EC/EG do not have BE.**

Estimate the proportion of patients negative via EC/EG who subsequently are proven negative via EGD. This would be measured by offering EGD to a proportion of patients who are EC/EG negative.

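### The Aim 2 miss-rate precision (0.5% ±1.4%, 1% ±2%) is a normal approximation on about one expected event or fewer and is too favourable; the rates are also labelled with the wrong denominator

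*Combined protocol and SAP*

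**What the plan says.** Section 2.0 heads Aim 2 "Confirm that patients who are negative as assessed by EC/EG do not have BE". The sentence beneath it is milder: it sets out to estimate the proportion of EC/EG-negative patients who prove negative at EGD. Section 9.0 lists this as Primary Aim 2 and calls for a proportion. Primary Aim 1 is to be reported with 95% confidence intervals. For Primary Aim 2 no interval, interval method or maximum acceptable miss rate is given.

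The sample size justification in Section 9.0 plans up to 100 research EGDs in test-negative patients. Assuming 5% prevalence and 90% sensitivity, it says "the expected rate of missed BE will be 0.5% in EsoGuard negative patients", and that with 100 EGDs "we will be able to estimate a miss rate of 0.5% with a 95% confidence of" ±1.4%. For 80% sensitivity it gives 1% ±2%, again as a rate in EsoGuard-negative patients.

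**The concern.** A symmetric ± around a rate of 0.5% or 1% in 100 patients crosses zero, which suggests a large-sample formula used where almost no events are expected. The rates themselves look like prevalence multiplied by one minus sensitivity. That is a share of everyone screened, not of those who test negative.

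Aim 2 is a primary aim, and these two lines are the only statement of what 100 research EGDs can show. A reader would take from them that the miss rate will be bounded at about 2% to 3%. If the attainable bound is higher, any reassurance drawn from a negative test is weaker than the plan suggests.

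**Working it through.** **Inputs**, all from the sample size justification in Section 9.0: prevalence 5%; sensitivity 90%, or 80% in the pessimistic case; specificity 90% ("with a 90/90 sensitivity/specificity for the EsoGuard assay(26), then 70 would undergo endoscopy"); 500 recruited ("We propose to recruit 500 patients for EC/EG"); 100 EGDs in test-negative patients. The 90% specificity is stated for the PPV calculation. I carry it over to the miss rate in both sensitivity cases.

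**1. Reproduce the stated precision.** Normal-approximation half-width = 1.96 × √(p(1 − p)/n), n = 100.
- p = 0.005: 1.96 × √(0.005 × 0.995/100) = 1.38%, printed as ±1.4%. Implied interval -0.9% to 1.9%.
- p = 0.01: 1.96 × √(0.01 × 0.99/100) = 1.95%, printed as ±2%. Implied interval -1% to 3%.

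The plan's arithmetic is therefore right for the formula used. A continuity-corrected version gives ±1.88% and ±2.45% and does not match.

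**2. Reproduce the stated rates.** 5% × 10% = 0.5% and 5% × 20% = 1%. These are missed cases divided by all patients screened.

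**3. Rate among test-negatives.** Missed/(missed + true negatives), with 500 patients, 25 with BE and 475 without. True negatives = 475 × 0.90 = 427.5.
- Sensitivity 90%: missed = 25 × 0.10 = 2.5; 2.5/(2.5 + 427.5) = 2.5/430 = 0.58%.
- Sensitivity 80%: missed = 25 × 0.20 = 5; 5/(5 + 427.5) = 5/432.5 = 1.16%.

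The same half-width formula at these rates gives ±1.49% and ±2.10%, so the denominator alone changes little.

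**4. Expected events in 100 EGDs.** 0.58 and 1.16. The chance of seeing none is (1 − 0.0058)^100 = 56% and (1 − 0.0116)^100 = 31%. A rate of 0.5% cannot itself be observed in 100 patients; the possible results are 0%, 1%, 2% and so on.

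**5. Limits the study can report.** Exact (Clopper-Pearson) two-sided 95%. For zero events the upper limit is 1 − 0.025^(1/100) = 3.6%.

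| Misses in 100 | Exact 95% limits |
|---|---|
| 0 | 0 to 3.6% |
| 1 | 0.03% to 5.4% |
| 2 | 0.2% to 7.0% |

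Other small-sample intervals differ somewhat. The Wilson upper limits are 3.7%, 5.4% and 7.0%. The Jeffreys upper limits are 2.5% for 0/100 and 4.6% for 1/100.

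**6. Compare.** In the 1% scenario the matching result is 1/100: implied upper limit 3%, exact 5.4%, Jeffreys 4.6%. In the 0.5% scenario the implied upper limit is 1.9%, yet even the best possible result, 0/100, gives 3.6% exact or 2.5% Jeffreys.

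**The case against.** The strongest reply is that these are planning figures that reproduce exactly, that the plan promises no upper limit, and that Aim 2 carries no test, threshold or decision rule. Clopper-Pearson is also conservative: at 0/100 the Jeffreys upper limit is 2.5% and the one-sided exact 95% limit is 2.95%, both inside the 2% to 3% a reader would infer. All of this is fair. It makes the choice of interval open and the fault one of method rather than calculation. It does not rescue the ± figures: none of the two-sided small-sample intervals considered reaches 1.9%, even with no misses.

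Four stronger readings are tempting, and the documents do not support them.
- *One missed case would leave enrichment unproven, because 5.4% exceeds the assumed 5% prevalence.* The plan defines enrichment as test-positive against test-negative patients. On its planned counts, 22/70 against 1/100 gives a Fisher p of about 5 × 10⁻⁹. And 0/100 would itself be unlikely if test-negatives carried BE at 4% to 5% (probability 1.7% to 0.6%).
- *Sensitivity could be as low as 59% after 0/100.* That adds 3.6% × 430 = about 15.6 misses to 22.5 detected cases, hence 38.1 cases in 500, a prevalence of 7.6%, above the plan's 4-6%. Holding prevalence at 5% gives about 36% instead. The figure turns on an assumption the plan does not make.
- *The analysis would report 0 ±0 in most trials.* No interval method is specified for the Aim 2 analysis, so this would attribute to it a formula seen only in the planning text.
- *The aim itself is to prove absence of BE.* Only the heading says so; the text beneath it already speaks of estimating. No finite sample could prove a zero rate.

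**Conclusion.** The point holds in a limited form. The stated Aim 2 precision is not valid at these event counts and is too favourable: exact upper limits are 3.6%, 5.4% and 7.0% for 0, 1 and 2 misses, against implied upper limits of 1.9% and 3%. The denominator label is also wrong, but by little: 0.58% rather than 0.5%, and 1.16% rather than 1%. The interval method and the sample of 100 drive the conclusion, not the denominator.

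This rests on two-sided 95% intervals, 5% prevalence, 90% specificity and all 100 research EGDs being completed. The plan says up to 100, so the limits would be wider with fewer; for illustration, 0/50 gives an exact upper limit of 7.1%. Nothing here calls the enrolment target or the conduct of the study into question.

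**What to change.** In the sample size justification of Section 9.0:
- restate the expected miss rates as 0.58% and 1.16% of EsoGuard-negative patients;
- replace ±1.4% and ±2% with exact limits, or those of another named small-sample method, for 0, 1 and 2 misses in 100.

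Under Primary Aim 2 in Section 9.0, state that the proportion will be reported with that same 95% interval and that the conclusion about missed BE will go no further than its upper bound.

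Changing the verb in the Aim 2 heading of Section 2.0 to match the text below it is optional.

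The cost is a few sentences of wording and a less favourable precision statement. No added patients or procedures are needed.

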## **10.0 PATIENT CONSENT AND PEER JUDGEMENT**

All institutional, NCI, FDA, state and Federal regulations concerning informed consent and peer judgment will be fulfilled.

## **11.0 RECORDS TO BE KEPT**

To ensure confidentiality for patients participating in the study, numbers will be assigned to each subject. Each study coordinator and PI has access to participant identifiers and the assigned numbers at their respective institutions. Questionnaire information will be identified by a code number. All subject records (hard copy) will be stored in locked file cabinets at the institution where the patient was enrolled. All coded information (questionnaire data, pathology reports, surgical reports, endoscopy reports and lab analysis results) collected about a participant will be entered into Labmatrix and Veeva Vault, secure electronic databases. The information stored in these databases is protected under HIPAA and all individuals with access to the information follow government regulations to protect the privacy of research study subjects.

If participants are patients at the institution where they are recruited, results from research and other information obtained during the study will not be placed in the patient's medical record. If standard of care lab test results are confirmed in a CLIA laboratory it is appropriate to include those results in the patient's medical record. Esoguard and possible research EGD results will be shared with research participants and their physician. Esoguard results will be placed in EMR by study investigators and copied to the primary physician. Patients will also be called by phone with results.

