7. Selected patients whose EsoGuard assay comes back negative will also be offered a research EGD if they consent. . EsoGuard assay results may take up to two weeks from the date when the sample is obtained. Patients will be contacted by phone and results will be discussed with them. If the patient chooses, they will then have the opportunity to schedule an EGD at their convenience. This will be a research EGD.
8. Patients who participate in the research study and undergo EC/EG will be provided \$20 as a token of appreciation along with a parking pass. In addition, those who are EC/EG negative and undergo a research EGD will be offered \$60 as an additional token of appreciation along with a parking pass.

The study Questionnaire obtains details regarding GERD symptoms, environmental exposure history, family history, height, weight, and prior upper endoscopy along with attitudes toward non-endoscopic screening. The questionnaire will take approximately 5 to 15 minutes to complete. The gastroesophageal reflux questionnaire (GERQ) is a validated measure of reflux symptoms and environmental exposure history developed by the Mayo Clinic(24).

The EsoCheck procedure is performed according to its Instructions for Use (Appendix 1). Samples collected are sent by study coordinators to ResearchDx/PacificDx, a licensed CAP/CLIA Laboratory, [name] where the EsoGuard assay will be performed. The EsoGuard test extracts DNA from the esophageal samples. DNA is reduced with bisulfite and then assayed for methylated Vimentin and methylated CCNA1 using specific primers. % methylated Vimentin > 2% or % methylated CCNA1 > 0.5% is considered positive.

Patients who have a positive EsoGuard assay will then be offered and undergo standard of care EGD. They will be informed that this endoscopy will be billed to insurance. EsoGuard is an approved laboratory developed test. Up to 100 patients who have a negative EsoGuard assay will also be offered a research EGD free of charge if they choose to participate further in research. Patients with BE or EAC at EGD will have standard of care screening and diagnostic biopsies. Biopsies from BE and EAC will be directed by using high definition narrow band imaging. Biospecimens will also be snap frozen at bedside and stored for future research assays.

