## 9.0 STATISTICAL CONSIDERATIONS

EsoCheck/EsoGuard positive will mean the reporting of a “positive” result for an EsoGuard test run on a sample obtained via EsoCheck. EGD positive will mean a result of BE (whether or not dysplasia is also present) and/or EAC based on the visualization of salmon-colored mucosa on EGD as well as the reported pathologic finding of intestinal metaplasia, dysplasia and/or neoplasia.

A two by two table will be constructed comparing results from EC/EG and result from EGD histology.

	EGD Positive	EGD Negative	Total
EsoCheck/EsoGuard Positive	$PP$	$PN$	$PP+PN$
EsoCheck/EsoGuard Negative	$NP$	$NN$	$NP+NN$
Total	$PP+NP$	$PN+NN$	$n$

where

$PP$  is the number of patients who test positive via EsoCheck/EsoGuard then positive via EGD,  $PN$  is the number of patients who test positive via EsoCheck/EsoGuard then negative via EGD,  $NP$  is the number of patients who test negative via EsoCheck/EsoGuard then positive via EGD,  $NN$  is the number of patients who test negative via EsoCheck/EsoGuard then negative via EGD.  $n = PP+PN+NP+NN$  and represents the total sample size.

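### No masking of the endoscopist or pathologist to the EsoGuard result is specified, which can bias the estimates, most plausibly upward and mainly for PPV

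*Combined protocol and SAP*

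**What the plan says.** All places are in the combined protocol and SAP.

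- **Order of tests.** Section 7.0, items 6 and 7: the EsoGuard result may take up to two weeks, the patient is told it by phone, and EGD is scheduled after that.
- **EsoGuard positive.** Item 6: "Patients whose EsoGuard assay results comes back positive, suggesting that they may have BE, will be recommended an EGD", and "This will be a standard of care billable EGD".
- **EsoGuard negative.** Item 7, for selected patients who agree: "This will be a research EGD". Section 9.0 limits this to 100 patients and bills it to research.
- **Medical record.** Section 11.0: "Esoguard results will be placed in EMR by study investigators and copied to the primary physician". The same paragraph says, for patients of the recruiting institution, that "results from research and other information obtained during the study will not be placed in the patient's medical record". A sentence between the two admits standard-of-care laboratory results confirmed in a CLIA laboratory. That may be the intended link, but the text does not say so.
- **Reference standard.** Section 9.0 defines EGD positive as BE and/or EAC by "visualization of salmon-colored mucosa on EGD as well as the reported pathologic finding of intestinal metaplasia, dysplasia and/or neoplasia".
- **Sampling.** Section 7.0: "Patients with BE or EAC at EGD will have standard of care screening and diagnostic biopsies". Routine-histology biopsies every 2 cm are described for patients found to have BE. Up to 12 further brushings or biopsies are planned in normal esophagus and BE alike, for research and control purposes.
- **Masking.** No section keeps the EsoGuard result from the endoscopist or pathologist, standardises the biopsy requisition, or provides an independent read.

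**The concern.** When the reference standard is a judgement and the reader can know the index test result, the index test can influence the standard it is measured against. Here the visual call is one half of the definition, and it also decides who has diagnostic biopsies. An endoscopist who knows that EsoGuard is positive may call an irregular junction columnar mucosa and biopsy it, and a pathologist aware of the result may report borderline metaplasia more readily. That raises PP. In a patient known to be negative, a short segment may be passed over and never sampled for diagnosis, which lowers NP. Both primary aims in Section 9.0 are computed from these cells: Aim 1 is PP/(PP+PN), and Aim 2 is the EGD-negative share of the EsoGuard-negative row. Section 9.0 also sets a minimum PPV of 20%, so a shift of a few calls could matter to how the result is read.

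**Working it through.** **Inputs (Section 9.0):** N = 500; prevalence 5% or 4%; sensitivity and specificity 90%; 100 research EGDs in negatives; PPV threshold 20%.

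**1. The plan's own figures.** TP = N × prevalence × sensitivity; FP = N × (1 − prevalence) × (1 − specificity); PPV = TP/(TP + FP).
- 5% prevalence: TP = 500 × 0.05 × 0.9 = 22.5; FP = 475 × 0.1 = 47.5; 70 EGDs; PPV = 22.5/70 = 32.1%. The plan states 70, 22 and 32%.
- 4% prevalence: TP = 18; FP = 48; 66 EGDs; PPV = 18/66 = 27.3%. The plan states 66, 18 and 27%.
- Miss rate at 5% prevalence: FN = 2.5, TN = 427.5, so 2.5/430 = 0.58%. The plan states 0.5%.

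All agree within rounding.

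**2. Over-calling among EsoGuard positives.** Let q be the share of BE-free EsoGuard positives recorded as EGD positive. The documents give no value for q; 2%, 5% and 10% are assumptions. Apparent PPV = (TP + q × FP)/(TP + FP).

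| q | 5% prevalence | 4% prevalence |
|---|---|---|
| 0 | 22.5/70 = 32.1% | 18/66 = 27.3% |
| 2% | (22.5 + 0.95)/70 = 33.5% | (18 + 0.96)/66 = 28.7% |
| 5% | (22.5 + 2.375)/70 = 35.5% | (18 + 2.4)/66 = 30.9% |
| 10% | (22.5 + 4.75)/70 = 38.9% | (18 + 4.8)/66 = 34.5% |

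**3. Position against the 20% threshold.** Section 9.0 does not name an interval method, or say whether the point estimate or the lower limit must clear 20%. Taking the exact binomial 95% interval for PP/(PP+PN):
- 21/70: lower limit 19.6%
- 22/70: lower limit 20.9% (interval 20.9% to 43.6%)
- 18/66: lower limit 17.0%; 21/66: lower limit 20.9%

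At 70 EGDs one call separates the two sides of 20%; at 66 EGDs, three over-calls take 18 to 21 and across it. With a Wilson interval at 70 EGDs the crossing lies one call lower, between 20/70 (19.3%) and 21/70 (20.5%).

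**4. Under-detection among EsoGuard negatives.** Let m be the share of BE in negatives that is overlooked (assumed). Apparent miss rate = 2.5 × (1 − m)/430:
- m = 10%: 0.52%
- m = 25%: 0.44%
- m = 50%: 0.29%, so NPV moves from 99.4% to 99.7%

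Even at m = 100% the gain in NPV cannot exceed 0.58 percentage points. At 80% sensitivity the ceiling is 5/432.5 = 1.16 points. The plan's own half-width for 100 EGDs is ±1.4%. With perfect reading, the chance of no missed case in 100 is (1 − 0.0058)^100, about 56%, so an observed zero would say little about review bias.

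**The case against.** - **The pathologist.** A reader might infer that histology is read with the EsoGuard result known. The documents do not say what the pathologist is told or sees, and Section 11.0 gives no time for the EMR entry and contains the contrary sentence quoted above. What stands is that nothing prevents it. For the endoscopist, the type of EGD will usually reveal the result.
- **Certainty and direction.** A reader might infer that both estimates are biased in the test's favour. That is plausible, not shown. A visual over-call alone cannot create a PP, because pathology is also required. In negatives, the research EGD exists to find BE that the strategy missed, so an endoscopist might search harder there.
- **Research samples.** Columnar-appearing mucosa may be sampled in a normal esophagus in either group. This is a partial safeguard at most: the samples are for research and control, and Section 9.0 does not say they count toward EGD status.
- **Triage use.** Section 1.0 presents EC/EG as a triage step, and in that use the endoscopist knows the test is positive. An unmasked yield is therefore a defensible target for Aim 1, if the plan said so. The argument does not reach Aim 2.
- **Later repair.** It would be too strong to say that no later analysis could help. The release form in Section 7.0, item 3, covers pathology reports, slides and blocks, so a masked re-read could address the histology. It could not recover the visual call or tissue never sampled.
- **Size.** The 32.1% to 35.5% shift lies well inside the exact interval for 22/70. That is true, but a systematic shift is not reflected in a confidence interval.

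**Conclusion.** The point holds as a gap in the design: no masking is specified, the EsoGuard result is available through the EMR and implied by the type of EGD, and the reference standard includes a judgement that also governs diagnostic sampling. This can bias the estimates, most plausibly upward.

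It is mainly a PPV concern. The illustrated rise is 1.4 to 6.8 points at 5% prevalence, and it matters most if the lower limit is read against 20%. That size rests on the assumed over-call rates and on the plan's 90/90 accuracy; the documents give no basis for estimating the true rate. For NPV the possible gain is under 0.6 points on the main inputs. It would be wrong to give the two estimates equal weight, or to say that bias has been demonstrated. No sample-size figure changes.

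**What to change.** In Sections 7.0 and 9.0, state that:

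1. Diagnostic biopsies from both EsoGuard groups go to the existing pathologist under a study code, with the same neutral indication and without the EsoGuard result.
2. The study diagnosis is recorded before the pathologist consults the EsoGuard result, and this reading classifies EGD status in the two by two table. A neutral requisition alone would not mask a pathologist who has EMR access, so the order of recording has to be written down.
3. The endoscopist completes the same form in both groups (columnar mucosa present or absent, extent, image) before pathology is known.
4. The report gives as a limitation that the endoscopist could not be reliably masked. Hiding a billable procedure that was recommended because of the result is largely unworkable.

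In Section 11.0, reconcile the two sentences on what enters the medical record.

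Cost: a small workflow change at each site, and less clinical detail on the requisition until sign-out. No additional reader or procedure is needed, and nothing is withheld from the patient or the primary physician.
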